## **Interventions:**

### **Transcranial Direct Current Stimulation (tDCS)**

Previous reports suggest heavy drinking is related to dysfunction in brain regions related to attention and inhibitory control (Ahmadi et al., 2013) and that activation of the inferior frontal gyrus results in improved learning ([name] et al., 2010), tDCS will be applied over right inferior frontal gyrus (rIFG) implicated in inhibitory control and avoidant behavior (e.g., Aron, 2007). According to standard tDCS procedures, saline or gel soaked electrodes will be placed on the scalp, and will be held in place with an armband. Similar to the methods we have previously used, the anode will be placed on the scalp over the rIFG and the cathode will be placed on the contralateral shoulder. The electrodes will deliver a very weak electrical current that may briefly result in an itching or tingling sensation. TDCS will begin 5 minutes before the beginning of meditation, during which participants will rate physical sensations associated with application of tDCS; if participants rate sensations as anything higher than persistent itching, the session will be terminated. Participants in the Active tDCS condition will receive 2.0 mA for 30 minutes of stimulation during the training session. Participants in the Sham tDCS condition will receive a 30 second ramp-up of current to up to 2.0 mA to provide an initial sensation and then the system will ramp-down to 0.0mA for the remaining 30 minutes. Upon completion of the last MBRP + tDCS session, participants will be queried whether they think they received real tDCS or sham.

tDCS equipment consists of either an Soterix Medical 1 x 1 Transcranial Direct Current Model mini-Clinical Trial Stimulator (Model 1601) or an Activa Dose II Iontophoresis Delivery Unit generator with a nine-volt battery, electrode wires and rubber electrodes, easy pad sponge electrode covers (for Soterix Medical) or rubber covers (Active Dose II), and latex-free, self-adherent bandages, coban (head wrap for Active Dose II) or elastic fasteners (Soterix Medical), in order to ensure safe and comfortable conduction of current to the subject. The procedure ensures that no metallic equipment will make contact with participants while tDCS is active. The Soterix Medical 1 x 1 and Active Dose II are not FDA approved for intended use, however the device poses non-significant risk (NSR) and we have used the

Active Dose II device safely on over 1000 participants in our prior research studies. The Soterix Medical 1 x 1 tDCS Model 1601 has also been used in several research studies. We will closely monitor the Soterix Medical Model 1601 device and if we experience any adverse events then we will discontinue use and notify the IRB immediately.

We will use both tDCS devices in this study for two reasons. First, we will have 10 of the Soterix Medical units and 8 of the Activa Dose II units. We will run groups of 8-12 and may need to supplement the Soterix Medical units with an Activa Dose II unit if all 12 participants attend a group. Second, if we have any equipment problems with the Soterix Medical units then we will be able to continue running the two year study with the Activa Dose II units. Third, we have not used the Soterix Medical units in prior trials and if we do experience adverse events with the Soterix Medical units then we will continue treatment with the Activa Dose II units.

### **Mindfulness Based Relapse Prevention**

MBRP therapists will have at least a Master's degree in psychology or related field or have a Bachelor's degree in Psychology and be enrolled in an American Psychological Association-approved Clinical Psychology doctoral degree program, and experience with group treatment of AUD. Therapists will be trained and supervised by [name], a licensed clinical psychologist with experience in MBRP therapist training and supervision. All MBRP sessions will be audio-recorded for supervision purposes and will be coded for adherence and competence using the MBRP-Adherence and Competence Scale. All treatment sessions will be 2 hours, with the first 30 minutes consisting of tDCS and guided meditation practice. After tDCS, sessions will include discussions of mindfulness as a means of coping with craving, cognitions, and emotions, role play exercises, and mindfulness practice. Participants will be given audio format files (e.g., mp3 players or CDs) developed specifically for MBRP for mindfulness practice outside of sessions.

### *VI. Study Timelines*

Screening and informed consent will take approximately 30 minutes. We anticipate that baseline and post-treatment behavioral testing sessions will require up to 5 hours each (approximately 10 hours total). The 2-month follow-up assessment will not include EEG and is expected to take 2 hours. The MBRP + tDCS interventions will require 2 hours and 30 minutes per session, including 30 minutes for initial questionnaires and withdrawal assessments, 15 minutes for tDCS setup, sensation checks, and cleanup at the end, 30 minutes for the tDCS, and 75 minutes for the MBRP intervention content. Thus, total participation time for MBRP + tDCS will be 16 hours over up to 8-weeks. Total participation time, after screening and consent, will be up to 32 hours.

### *VII. Study Location(s)*

Assessments and intervention sessions will take place in the Psychology Clinical Neuroscience Center in Logan Hall, Department of Psychology, University of New Mexico. Data analysis will be done at Logan Hall, Department of Psychology, University of New Mexico in offices maintained by PI [name].

### *VIII. Participant Compensation*

We propose an incentive structure to maximize compliance that is consistent with other successful tDCS studies conducted by the investigative team. Participants will be paid up to \$20/hour for their participation during assessments: baseline (up to \$100), session questionnaires during 8-sessions of treatment (\$80), post-treatment (up to \$100), and 2-month post-treatment (up to \$40), plus an additional \$10 bonus for completing the post-treatment assessment, a \$20 bonus for completing the 2-month follow-up assessment, and a \$50 bonus for completing all assessment sessions, making the maximum compensation \$400. To increase retention, participants will be asked to provide addresses,

phone numbers, and email addresses, as well as the names and phone numbers for friends and family members who “*will always know where you are.*” We have used these methods in our prior studies and achieved 87.5% or greater follow-up rates.

## IX. *Study Resources*

The Psychology Department is located in Logan Hall on the south edge of The University of New Mexico’s main campus. This 55,334 square foot, three story building is comprised of faculty, staff and graduate student office space, four classrooms, a library, a conference room, an undergraduate student computer lab, a graduate student computer lab, and human research and/or animal research facility lab space.

In May 2010 the Psychology Department was awarded a grant from NIH for almost \$5,000,000 as part of the Recovery Act Limited Competition: Core Facility Renovation, Repair, and Improvement. The funds were used to renovate the Psychology Department’s neuroscience research space into a state-of-the-art Psychology Clinical Neuroscience Center (PCNC). The PCNC, directed by Co-I [name], is a Category-I center in the Department of Psychology at UNM. This 10,000 square foot, \$5.5 million renovation includes 5 research pods containing offices for over 20 personnel, 4 imaging laboratories, 3 meeting rooms, and a data processing laboratory and classroom for up to 20 students with computer systems for each. Administrative resources include offices for the PCNC Director and for a Program Coordinator, as well as offices for a Computer Programmer and IT Manager.

### **Space**

Laboratory The PCNC has separate pediatric and adult electroencephalography (EEG) core laboratories (described in detail below), a neurostimulation core laboratory, a large computer core laboratory and a dedicated imaging computer room for data acquisition and analysis for EEG, along with imaging and stimulation laboratories of individual faculty.

Clinical Within the PCNC, three private assessment rooms (all equipped with closed doors and sound screens) are available to research staff.

Office [name] has a private faculty office, as well as four individual Research Assistant offices and access to a conference room.

Meeting Space The PCNC offers multiple group meeting locations to facilitate research. Rooms will accommodate groups from 10 to 40 participants. The rooms are available for investigator and team meetings, research seminars and other research gatherings. Smaller private rooms are available for small group meetings and one-on-one participant and stakeholder interactions.

### **Personnel Resources**

All study staff will be trained in recognizing signs and symptoms of intoxication as well as withdrawal symptoms. The UNM Psychology Department is located less than 1 mile away from several hospitals, including the UNM Hospital Emergency Department. The PI is a licensed clinical psychologist with extensive experience in the prevention and treatment of substance use disorder. The PI will train and supervise research staff and the study therapists to utilize data provided at each assessment point as well as clinical judgment to monitor and evaluate the condition of participants.

## **EXPECTED RISKS/BENEFITS**

---

### I. *Potential Risks*

There are only minor risks associated with participation in this study. Potential risks of completing self-report and behavioral assessments include: 1) some discomfort associated with the nature of interview questions; and 2) breach of confidentiality. Potential risks of tDCS include: 1) skin damage (rare) or skin irritation; 2) neural tissue damage (rare); 3) pain (rare); 4) alterations in mood or affect (rare); and 5)

electrical shock (rare). As enumerated below, we will take every possible step to reduce risk and discomfort to research participants.

## **Protections Against Risk**

**General Protections.** All study staff will be trained in recognizing signs and symptoms of intoxication as well as withdrawal symptoms. The UNM Psychology Department is located less than 1 mile away from several hospitals, including the UNM Hospital Emergency Department. The PI is a licensed clinical psychologist with extensive experience in the prevention and treatment of substance use disorder. The PI will train and supervise research staff and the study therapists to utilize data provided at each assessment point as well as clinical judgment to monitor and evaluate the condition of participants.

**Assessment Protections.** While the nature of the research dictates that data cannot be collected anonymously, additional safeguards will be put in place to protect against breach of confidentiality. Each participant will be assigned a unique ID code at screening. After phone screening, the phone screening form will be destroyed for those who are not eligible. First and last names of those who are screened out will be maintained in order to identify individuals who attempt to re-screen. De-identified demographic information and reasons for ineligibility for those who are ineligible will be recorded in a separate document without identifiers for reporting purposes. Eligible individuals will be scheduled for a baseline assessment session and their phone screening form will be de-identified and only linked to the participant with the participant ID. Contact information for participants who are screened in will be maintained in a password protected file. All assessments for a given participant will be coded with his/her ID code. Questionnaire data will be collected using Mind Research Network COINS system, hosted on a secure Mind Research Network server supporting 128-bit encryption and protected electronically using the most up-to-date security software available. Other data will be retained at the UNM Psychology Clinical Neuroscience Center (PCNC) in locked file cabinets and on password protected electronic files on computers with restricted access. A single master list linking participant names and ID codes will be stored onsite in a separate locked file cabinet, and will only be available to research staff. Further, a Certificate of Confidentiality, which provides additional protection against obligatory release of confidential information, will be obtained from the Department of Health and Human Services prior to participant recruitment.

**EEG Protections.** EEG is considered a safe and noninvasive procedure. There is some risk of seizure during EEG among individuals with seizure disorders, so we will be excluding any participants with a history of seizures or seizure disorder. Participants will be monitored throughout the procedure. If there is any discomfort, the procedure will be discontinued. The PCNC has facilities available to wash off the EEG gel.

**tDCS Protections.** Normal patient handling procedures are followed to eliminate risks. The participants will be able to communicate with the investigators at all times. The participant's emotional state, mood, and physical sensation will also be monitored with a questionnaire administered before, during, and after the tDCS procedure. The following potential risks that could be associated with transcranial direct current stimulation have been identified and we address them below. We have conducted over 1200 tDCS sessions using the Activa Dose device in our lab and experienced only one adverse event, which was a minor skin burn resulting from an exposed wire. Since the adverse event we have shrink-wrapped all of our wires (see Figure 2a and 2b below) and have experienced no other events. The Soterix 1x1 Mini-CT units were designed for clinical trials and have been tested in numerous treatment studies and clinical trials (<http://soterixmedical.com/>). All devices were designed by bioengineers using medical grade materials.

Figure 2a. Electrode setup for tDCS.

Figure 2b. Shrink-wrapped wires and banana plugs.

Pain. A very strong, focal current density can result in pain. We will be using large electrodes and weak electrical current. With protocols similar to ours, most participants report only mild, transient tingling at the stimulation site resulting from tDCS. Any participant report of pain resulting from tDCS will result in immediate termination of stimulation.

Alterations in mood or affect. There is evidence that tDCS can result in changes in mood. While no studies have reported negative mood resulting from DC stimulation, several studies have reported improved mood after tDCS. It should be noted that in these studies stimulation was applied for significantly longer durations. Studies designed to investigate the safety aspects of tDCS have reported no significant changes in mood as measured with the visual analogue mood scale and no significant changes in measures of fatigue when comparing stimulation to sham. Participants will receive 90 minutes of group mindfulness treatment after stimulation is discontinued and the group clinician will monitor the mental state of all participants throughout the group treatment.

Neural tissue damage. At very high current densities and long durations of stimulation there is a possibility that DC stimulation can result in neuronal tissue damage due to neuronal hyperactivity or brain tissue heating. In our study, we propose to use electrodes with at least 3.3 X 3.3 cm^2 sponge/skin contact to induce 2 mA stimulation resulting in a maximum current density of 0.19mA/ cm^2 at the scalp surface. Most likely, 90% of this current will be shunted through the cerebrospinal fluid and the skin. Current distribution models of DC stimulation suggest that 2mA current at the scalp surface will result in a maximum current density of 0.00986 mA/ cm^2 in the brain. While this current density is enough to elicit a transient modulation in cortical excitability, it does not elicit tetanic and/or suprathreshold excitation necessary to cause neuronal damage. Brain tissue heating is also insignificant for this level of stimulation. Moreover, the duration of stimulation specified in our design (~30 minutes) is well within the bounds of normal procedures. Protocols similar to ours do not reveal changes in structural magnetic resonance images or pathological EEG signals resulting from tDCS. For these reasons, we believe that our stimulation protocol is within safe parameters and that the possibility of neuronal tissue damage is extremely unlikely.

To minimize any possible tissue damage, participants will fill out a tDCS sensation questionnaire form throughout the tDCS procedure. This questionnaire allows us to monitor what the participants are physically feeling (including sensations of “itching,” “heat/burning,” and “tingling”) at the electrode sites. This will be given at the following time points: approximately 1 minute after start of tDCS, approximately 5 minutes after start of tDCS, and approximately 20 minutes after start of tDCS. If at any time the participant reports a sensation level of 7 or above, based on a 10 point scale, we will immediately discontinue the stimulation. In addition, participants are instructed to tell us at any time if the sensations are uncomfortable or if they would like the tDCS to be discontinued for any reason.

Skin damage or irritation. There is a slight risk of skin damage or irritation resulting from tDCS stimulation. With the exception of one study that reported transient redness at the stimulating electrode site in two men who had recently shaved their heads, we have encountered no reports of skin damage or irritation in any of the tDCS literature. Stimulation parameters similar to the ones proposed in the application have not resulted in skin damage in our previous studies. We will be using at least 3.3 X 3.3 cm^2 saline water or gel-soaked electrodes for our study which minimizes the possibility of chemical reactions at the electrode-skin interface and resultant skin damage. The scalps of each participant will

[figure not shown]
be visually inspected immediately before stimulation. Any identified irritation or evidence of recent shaving of the head will postpone that participant's participation in the study. Participants will be encouraged at the beginning of the tDCS procedure to report any pain or discomfort that they may encounter throughout the procedure. Any such reports, or evidence of redness or irritation of the scalp, will result in the immediate termination of stimulation. We have found in our recent work that saline water soaked electrodes have acceptable sensation ratings for most individuals, but for some individuals (particularly those with more sensitive skin) gel electrode solution reduces irritation. Thus, we include the option of either saline-soaked or gel soaked electrodes, which can further reduce skin irritation for some participants.

Electrical shock. As with any contact between persons and electrical apparatuses, there is a slight possibility of electrical shock. At UNM we have had no incidents of significant electrical shock resulting from DC stimulation, and we do not anticipate this event occurring in our experiment. One of the advantages of using the ActivaDose II stimulator (Figure 3) to induce DC current is that the current is obtained from a 9-volt battery and can be limited to a safe level. The Soterix medical stimulation (Figure 4) is powered by a lithium ion battery and the stimulation is capped at 2.5 mA from the device. Our testing of the Soterix device using a multimeter has indicated that when the Soterix unit is set at a certain mA that it never exceeds that voltage. Using either unit ensures that electrical shocks resulting from current surges will not occur. Further, we will ensure that participants are not in contact with any potential conductors other than those specified in the experimental design (e.g. the tDCS stimulator). This measure greatly reduces the likelihood that electrical shock will result from short circuiting or inadequate insulation.

Figure 3. ActivaDose II stimulator and electrode set-up with blinding box apparatus.

Figure 4. Soterix Medical 1x1 mini-CT tDCS stimulator with electrode set-up.

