**MBRP + tDCS Sessions (2 hour treatment groups + 30 minutes for initial assessments, breathalyzer, pregnancy tests, and withdrawal assessments).** Following the baseline session, participants will begin a series of weekly or twice weekly group MBRP + tDCS intervention sessions for up to eight weeks at the PCNC. To maximize the availability of groups and to accommodate various therapist schedules we will run groups either twice per week for four weeks or once per week for eight weeks. All participants will receive up to 8 two hour sessions of MBRP + tDCS, regardless of the group schedule.

At the beginning of each session the subject will be asked to complete a baseline mood assessment, all participants will be breathalyzed, and fertile female participants will be asked to complete a pregnancy test. Women who are pregnant will not be allowed to complete the study and will be told in private of their pregnancy status. Participants who have a BAC > 0.0 will be rescheduled, given snacks and water until their BAC is reduced to < 0.04 in accordance with NIAAA guidelines, and will be provided a taxi voucher. We will also assess all participants for potential alcohol withdrawal at the time of each tDCS session. If participants show significant signs of withdrawal and/or have a score of 8 or greater on the Clinical Institute Withdrawal of Alcohol Assessment Scale (CIWA), then the research assistant will recommend the subject go to the UNM Hospital for further assessment. Our previous studies with more severely dependent individuals occasionally encountered patients with severe withdrawal, and this protocol was used successfully without any adverse consequences. Subjects with CIWA scores of 8 or greater at any session will be excluded from the research study. These aspects of the study will take approximately 30 minutes to complete.

Subjects will then receive 30 minutes of either active or sham tDCS stimulation, depending on their group assignment. A sensation questionnaire will be administered after 5 minutes of tDCS, 15 minutes, and 25 minutes of tDCS. At the end of tDCS stimulation participants will be asked a few questions regarding their mood and mental state to make sure that they have no lingering effects of the stimulation. After tDCS stimulation the remaining time will be used for MBRP session content (described below).

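### The only scheduled skin look is at the scalp before stimulation; the cathode site, and all skin after electrode removal, rest on self-report whose timing the protocol states in three ways

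*Combined protocol and SAP*

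**What the plan says.** **Visual check.** Protections Against Risk, tDCS Protections, skin damage paragraph: "The scalps of each participant will" (a figure interrupts the sentence) "be visually inspected immediately before stimulation". Irritation found then postpones participation. During the procedure, "Participants will be encouraged at the beginning of the tDCS procedure to report any pain or discomfort that they may encounter throughout the procedure", and the paragraph continues: "Any such reports, or evidence of redness or irritation of the scalp, will result in the immediate termination of stimulation".

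**Electrode sites.** The tDCS intervention section says that "the anode will be placed on the scalp over the rIFG and the cathode will be placed on the contralateral shoulder". The Background places the cathode on the left upper arm.

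**Self-report.** The neural tissue damage paragraph describes a sensation questionnaire that asks about itching, heat or burning, and tingling at the electrode sites, in the plural. Its timing is given in three places (see working).

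**End of stimulation.** Procedures & Interventions, MBRP + tDCS Sessions: "At the end of tDCS stimulation participants will be asked a few questions regarding their mood and mental state". Skin is not named there.

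**Device rule.** For the Soterix Model 1601, the protocol promises close monitoring and says "if we experience any adverse events then we will discontinue use and notify the IRB immediately". The Unanticipated Problems/Adverse Events section requires a report to the IRB within 7 days of an event. It does not say how events are to be found.

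**The concern.** A rule that acts on any single adverse event is only as good as the means of finding events. Here the scheduled look covers one of the two electrode sites and comes before the exposure that could cause harm. The skin under an electrode can be seen properly when the electrode is lifted off, and the plan describes no look at that moment.

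The one tDCS adverse event the team reports from its own sessions was a minor skin burn, so this type of event has occurred in this setting. The Soterix units were not used in the team's earlier trials, and the decision to keep using them depends on what is recorded. Any closing statement about side effects by arm would rest on the same record.

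**Working it through.** The plan states no figure on this point, so there is none to reproduce. The check sets the passages side by side and counts scheduled looks.

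**1. What each safeguard covers**

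| Safeguard | Scalp (anode) | Shoulder/arm (cathode) | After electrode removal |
|---|---|---|---|
| Scheduled visual check | Yes, before stimulation | Not described | Not described |
| Redness trigger during stimulation | Yes, scalp named | Not named | Does not apply |
| Sensation questionnaire (self-report) | Yes | Yes | Depends on section |
| Spontaneous report of pain or discomfort | Yes | Yes | Encouraged during the procedure |
| End-of-stimulation questions in the session description | Mood and mental state | Mood and mental state | Skin not named |

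**2. Questionnaire timing**

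| Section | Time points |
|---|---|
| MBRP + tDCS Sessions | 5, 15 and 25 min |
| tDCS Protections, neural tissue damage | about 1, 5 and 20 min |
| tDCS Protections, opening paragraph | before, during and after |

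Stimulation lasts 30 minutes. The last point in the two minute schedules falls 30 − 25 = 5 or 30 − 20 = 10 minutes before it ends. Only the third statement includes a point afterwards.

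**3. Scheduled looks per participant**

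Inputs: one baseline stimulation and up to 8 treatment sessions; two electrode sites.

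- Stimulations if all are received: 1 + 8 = 9.
- Cathode site: 0 of 9 stimulations have a scheduled look, before or after.
- Scalp: the look before each of sessions 1 to 8 also shows any lasting mark from the preceding stimulation, so 8 of 9 are followed by a later look. The final one is not.
- Looks at electrode removal: 0 of 9 at either site.

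**4. Delay**

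Groups meet twice weekly for four weeks or weekly for eight, so the next scalp look comes about 3 to 7 days after a treatment session. In weekly groups that is about the 7-day reporting limit. The interval from baseline to session 1 is not stated. The post-treatment visit may fall up to two weeks after the final session, and Table 1 lists no skin check.

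**5. Why ascertainment matters to an any-event rule (illustration only)**

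Assume the earlier Activa Dose experience, 1 event in 1200 sessions, as the per-session rate. The protocol says over 1200 sessions, so this is an upper figure. Assume too that all 86 × 8 = 688 sessions use one device at equal risk, and that a share s of events is recorded. Then

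P(at least one recorded) = 1 − (1 − s/1200)^688

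- s = 1: 0.44
- s = 0.75: 0.35
- s = 0.25: 0.13

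The documents give no value of s. The range shows only that the rule is sensitive to it.

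**The case against.** The strongest reply is that self-report already covers the ground. The questionnaire asks about both electrode sites, any pain or discomfort is to be reported, and several triggers end stimulation. Participants then stay for 75 to 90 minutes of group treatment, depending on the section, with staff present. One section says physical sensation is also asked about afterwards. This stands in part: a painful lesion at the arm would probably come to light. It does not cover a painless lesion, one that appears later, or one after the final session that the participant does not mention. The timing of the questionnaire is itself unsettled.

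Three stronger readings are tempting, and the documents do not support them.

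- *Skin is observed only before stimulation and arm injuries are missed.* The redness trigger implies some watching of the scalp during stimulation, and self-report reaches the arm. Cathode-site detection relies on self-report; it is not absent.
- *Adverse events are undercounted.* No detection rate is given, and self-report might bring detection close to complete. An undercount is possible but not shown.
- *Only 44% of exposures are checked.* With 9 × 2 = 18 site-exposures, 8/18 = 44% have a later scheduled look. That is a count of appointments, not of detection. It gives self-report no weight and treats a baseline stimulation of under 10 minutes, or a sham ramp of 30 seconds, like 30 minutes of active current.

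It is also fair to say that the earlier burn came from an exposed wire on the other device and that the wires have since been shrink-wrapped. It therefore does not point to the cathode site. The any-event rule covers the Soterix units only. No planned efficacy estimate depends on skin findings.

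**Conclusion.** The point holds as a gap in safety ascertainment. No visual check of the cathode site is described, no skin check follows electrode removal, and the self-report that must fill both gaps has three different timings. Skin events may be under-ascertained, by an unknown amount.

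The firm part of the size is the count: no scheduled look at the cathode site, none at removal, and none at any site after the final session. It assumes that all sessions are received and that the described checks are the complete set. The probabilities in the illustration rest on an assumed rate and should not be quoted as estimates for this trial.

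The consequence falls on the Soterix any-event rule and on the reported safety record, not on the drinking outcome. This is a worthwhile, cheap improvement rather than an error that threatens the trial's main conclusion.

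**What to change.** 1. Word the skin check so that it names both electrode sites in the montage, and reconcile the two descriptions of the cathode position (shoulder; left upper arm).
2. Add a recorded look at both sites when the electrodes are removed, at the baseline stimulation and every session.
3. Reconcile the questionnaire timing across the session description and the two tDCS Protections paragraphs, and say whether there is a point after stimulation ends.
4. Keep the record away from outcome assessors, because redness could hint at allocation, and report findings by arm and device.

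These changes concern what is looked at and written down. What is done about a finding stays with the clinical team.

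**Cost.** One line on the session form and a brief look as the electrodes come off, with no extra staff. Study Timelines already allows 15 minutes for setup, sensation checks and cleanup. The session breakdown under Data Collection Procedures (30 + 30 + 90 = 150 minutes) shows no such slot, but the electrodes must be removed under either account. The downsides are that slightly more minor redness will be recorded, which raises the reported skin-event rate a little, and a small risk to the blind that item 4 limits.
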